2 INTRODUCTION

2.1 STUDY RATIONALE

SARS-CoV-2 virus has created one of the most challenging public health emergencies in modern history and antibody testing could be an important tool for responding to this pandemic. Uptake of SARS-CoV-2 testing in underserved populations is subject to barriers related to resources and behaviors that may differ within communities and even households. Testing for SARS-CoV-2 antibodies in underserved populations can play an important strategic role for several reasons. First, antibody testing is critical for public health surveillance and planning as it can identify both active and recovered infections. This helps us identify the extent of exposure in the community and learn more about illness severity and the mortality rate. This is crucial information for policy makers as they plan pandemic response to reduce disease burden and disparities. Second, antibody testing is also an important clinical tool and providers can choose from several FDA approved antibody tests with high specificity and sensitivity.¹ Finally, although the science is still uncertain, antibody testing might be used as a tool for identifying populations that can safely return to work or for prioritizing scarce PPE resources. However, antibody testing to date in the US has been limited. It is important to understand barriers and actionable facilitators of testing in underserved populations to address those most in need. We need to understand how to increase uptake of testing among vulnerable populations and how to encourage testing and retesting in general. Messaging, financial incentives, social and personal factors as well as the effect of learning of your first test results have implications for controlling the spread of the virus. A negative test result might promote prevention behaviors for people who thought they were previously infected.²

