Our study, which will enroll and track a representative cohort of 2,160 persons (540 family clusters) for SARS-CoV-2 antibodies and repeatedly test them for antibodies, is significant for several reasons. First, it will allow us to track the evolution of the pandemic in the largest federally qualified health center (FQHC) in the United States. Second, we will be able to observe how the risk of infection is evolving differently in low-income underserved populations as compared to the general population. Third, repeat antibody testing of those who were seropositive in the first wave of testing will allow us to test how well antibodies maintain their presence at a second test 6-months later. There is preliminary evidence that antibodies wane over time, however current evidence is limited to few studies and small sample sizes.³ Fourth, and most importantly for scalable, generalizable, findings, we will find actionable ways to motivate repeat testing and we will be able to tailor those ways to the social and behavioral characteristics of the persons being tested.

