2.3.2 KNOWN POTENTIAL BENEFITS

All participants will receive free serology testing. Demand for testing is very high and tests are relatively expensive. In addition, accurate knowledge of serostatus is a benefit for participants. If participants increase preventative behavior in response to antibody testing then the research will also benefit others in society by reducing the spread of COVID-19.

Answering the research questions for this study is critical for designing effective and equitable COVID-19 testing programs. This study will help understand the barriers to serology testing, which will be important as serology increasingly used to inform policy. It will also help the world understand how people respond to learning their serology test results, which will help us better understand how best to use testing as a policy tool. Finally, it will provide important evidence on how antibodies wane after acute exposure, how long they remain in the system, and whether people can be re-infected. In sum, the risks of this study are small relative to the potential benefits in identifying active and recovered COVID-19 infections for public health planning.

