4.2 SCIENTIFIC RATIONALE FOR STUDY DESIGN

Repeat testing for SARS-CoV-2 antibodies in disadvantaged communities will help identify active and recovered infections over time, and, as we learn about antibody protection, it may help identify persons who have immunity. Many questions about social barriers and behavioral facilitators remain unanswered.

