9.1 STATISTICAL HYPOTHESES

The figure below provides a conceptual diagram for thinking about what factors may influence testing take-up and retesting. Testing take-up would depend on several factors, including prior beliefs about infection, health literacy, information networks, health conditions, demographics and socio-economics. We have the following hypothesis based on analysis of literature on testing for HIV and Hepatitis as well as preliminary analysis of data from our prior study:

Hypothesis 1: Those who believe that they have been infected in the past would be more likely agree to testing to confirm that they have antibodies and potential immunity; **Hypothesis 2:** People with poor health literacy will be less likely to agree to testing as they might find it daunting to understand what the test does and how to interpret results; **Hypothesis 3:** Those who are risk averse would be more likely to agree to testing as it reduces uncertainty about serostatus; **Hypothesis 4:** Those with preexisting health conditions would be more likely to agree to testing as they face higher risks from COVID-19 and thus have more to gain from learning serostatus; **Hypothesis 5:** Minorities and those in lower socio-

economic strata would be less likely to agree to testing due to fear of discrimination, lack of trust in health care/research, poor past experience, and perception of being at low risk of infection. We also generate hypotheses for facilitators to retesting (r) relative to those who take a first test **Hypothesis 1r:** Persons who practice low COVID-19 mitigation, exhibit risk-seeking and have high exposure risk may respond to a lottery retest incentive. **Hypothesis 2r:** Those persons with low income, unemployed, or have high stress or anxiety may respond most to insurance of incentives. **Hypothesis 3r:** Persons who are sero+ at baseline will be less likely to return for a retest. **Hypothesis 4r:** Lottery insurance and family messaging will induce higher retesting rates. Hypotheses 1-5 are covariates that may affect agreeing to the test. Hypotheses 1r and 2r refer to heterogeneity of treatment effects for retesting, while 3r and 4r are main effects on retesting.

Conceptual diagram

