9.4 STATISTICAL ANALYSES

9.4.1 GENERAL APPROACH

Aim 1 (Hypotheses 1-5): Data from the baseline survey combined with data on which heads of households attended Time 1 testing will be used to address Aim 1. In particular, we will estimate logistic regressions where the dependent variable will be the binary indicator whether the head of household attended Time 1 testing (yes vs. no). The key independent variables will include: 1) prior COVID-19 testing, 2) which SARS-CoV-2 information sources are most trusted, 3) risk aversion, 4) heads of households or family member diagnosis of a health condition (e.g., diabetes, hypertension) and, 5) race/ethnicity, income, discriminatory incidences, household receipt of Supplemental Nutrition Assistance Program (SNAP) or Supplemental Security Income (SSI) benefits, and citing money as the biggest vaccine barrier.

$$\pi = \beta_0 + \beta_1 x_i + \varepsilon_i \quad [1]$$

$\pi = \ln\left(\frac{p}{1-p_i}\right)$; p_i , is the probability of attending Time 1 testing, by head of household i , and β_1 is each head of household reported social determinant of health. This will allow us to identify significant social and behavioral determinants for heterogeneity of effects (currently hypothesized in Hypotheses 1-5 above).

Aim 2 (Hypotheses 1r-4r): Aim 2 will involve regressing Time 2 retesting (yes vs. no) on the following items for Hypotheses 1r-4r: 1r) risk aversion, essential worker status, access to personal protective equipment, and risky forms of transportation (e.g., personal vehicle, carpool, bus), 2r) income, discriminatory incidences, employment status, whether heads of households personally, or other family members suffer from depression and/or mental health issues, and household receipt of Supplemental Nutrition Assistance Program (SNAP) or Supplemental Security Income (SSI) benefits, 3r) Time 1 seropositivity status and, 4r) the Financial Incentive and Messaging study arms.

$$\pi = \beta_0 + \beta_1 x_i + \beta_2 x_i + \beta_3 x_i + \varepsilon_i \quad [2]$$

For Hypotheses 1r-2r, $\pi = \ln\left(\frac{p}{1-p_i}\right)$, is the probability of Time 2 attendance by head of household i given they attended Time 1 testing; β_1 is the main effect of the head of household reported characteristic, β_2 is the main effect of the Financial Incentive, where the lottery condition is the reference, and β_3 is the interaction between the head of household reported social determinant of health and Financial Incentive.

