9.4.2 ANALYSIS OF THE SECONDARY ENDPOINT(S)

We will explore heterogeneity of treatment effects by using Model 2 to assess whether receptivity to study arm (e.g., personal messaging/loss protection) differs by significant social determinants of health identified in Hypotheses 1 through 5. To assess seroprevalence trends, we will use separate hierarchical models with a random household intercept to regress seropositivity status (yes vs. no), IgG value, and IgM value on testing time (Time 1 vs. Time 2).

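### Antibody trends are to be read as infection and waning, but the models contain only testing time and the plan does not say that vaccination is captured for each person tested

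*Combined protocol and SAP*

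**What the plan says.** The rationale treats serology as a marker of infection. Section 2.1 says of antibody testing that "it can identify both active and recovered infections", and section 4.2 says that repeat testing "will help identify active and recovered infections over time". Section 2.1 adds that retesting people who were seropositive in the first wave "will allow us to test how well antibodies maintain their presence at a second test 6-months later". Section 2.3.2 says of the study that "it will provide important evidence on how antibodies wane after acute exposure", and names re-infection as a further question it will inform. None of these sections mentions antibody produced by vaccination.

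The models that are to deliver this are in section 9.4.2: "To assess seroprevalence trends, we will use separate hierarchical models with a random household intercept". They "regress seropositivity status (yes vs. no), IgG value, and IgM value on testing time (Time 1 vs. Time 2"), with no other term. Section 9.1 states Hypothesis 3r: "Persons who are sero+ at baseline will be less likely to return for a retest". Its model in section 9.4.1 (Model 3) has Time 1 serostatus as the only predictor, again with a household intercept. Section 3 lists seropositive status in the primary row of the endpoint table.

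The only vaccine-related variable in the documents is an Aim 1 predictor in section 9.4.1, "citing money as the biggest vaccine barrier". It shows that vaccination was in view when the plan was written, but it does not measure who was vaccinated or when. The Schedule of Activities (1.3) has no vaccination entry. Section 5.5 says that one adult per household answers the survey and that minors do not. Section 6.3 gives a medical record number to AltaMed patients only, and no extraction of vaccination records is described. Section 2.3.3 refers to an Abbott assay without its target antigen.

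**The concern.** A coefficient for Time 2 against Time 1 measures change in antibody from any source. If the assay responds to vaccine antibody, someone vaccinated between the visits can turn positive without having been infected, and someone already positive can show a maintained or higher IgG value although infection-derived antibody has fallen. With testing time as the only predictor, the output cannot separate these cases from new infection or from persistence. Those are the readings that sections 2.1, 2.3.2 and 4.2 intend to make.

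At stake are the statements on how infection evolves in this population, on persistence at six months, on waning and on re-infection. Vaccination dates that are not asked for at the visits may be hard to recover later, especially for household members without an AltaMed record.

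**Working it through.** **Plan's own figures.** The plan projects no seroprevalence trend, so there is none to reproduce. The one usable input is 10% seropositive at baseline (table in 9.2). The same table gives a detectable difference of ±7 points covering Hypothesis 3r. It cannot be reproduced, because alpha, sidedness and the base retest rate are not stated, but this point does not dispute it.

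**Trend in seropositivity.** Inputs:
- Positive at Time 1: 10% (9.2), taken here as all due to infection.
- Interval between tests: six months (8.1).
- Share vaccinated between visits, v: not in the documents; assumed 10%, 30% and 60%, equal in positives and negatives.
- Share of vaccine responses the assay detects, d: not in the documents; assumed 95%, with 0% and 100% as bounds.
- No new infection, no waning, and the same people tested twice.

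Formula: Time 2 positive = 0.10 + 0.90 × d × v.

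| v | d = 0% | d = 95% | d = 100% |
|---|---|---|---|
| 10% | 10% | 0.10 + 0.90 × 0.95 × 0.10 = 18.6% | 19% |
| 30% | 10% | 0.10 + 0.90 × 0.95 × 0.30 = 35.7% | 37% |
| 60% | 10% | 0.10 + 0.90 × 0.95 × 0.60 = 61.3% | 64% |

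The whole rise in the last two columns occurs with no infection after Time 1.

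**Hidden waning.** Take the extreme case in which every Time 1 positive would have reverted to negative. With v = 10% and d = 95%, Time 2 positive = 0.95 × 0.10 = 9.5%. The time effect would then look almost flat against 10%, although no infection-derived antibody was still detectable.

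**Hypothesis 3r.** Model 3 compares the retest rates of Time 1 seropositive and seronegative people, which is what the hypothesis states. The arithmetic below concerns only a further step, reading that contrast as an effect of past infection. Assume 10% infected, a share v vaccinated before Time 1 independently of infection, full detection, infection lowering retesting by 7 points (borrowed from the ±7 in 9.2), and vaccinated-only people differing from seronegatives by δ points.

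Share of seropositives who were infected: f = 0.10 / [1 − 0.90 × (1 − v)]. Observed contrast = −7 × f + δ × (1 − f).

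| v | seropositive | f | δ = 0 | δ = +7 |
|---|---|---|---|---|
| 10% | 19% | 0.526 | −3.7 | −0.4 |
| 30% | 37% | 0.270 | −1.9 | +3.2 |
| 50% | 55% | 0.182 | −1.3 | +4.5 |

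The result runs from dilution to reversal, depending on v and δ, and the documents give neither. Every row also has more than the 10% seropositive that 9.2 plans for. The table shows what could happen and does not estimate the bias.

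**The case against.** The strongest reply is that much of this rests on silence and on facts outside the documents.

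- A reader might infer that vaccination is not recorded at all. The documents do not establish that. The survey instrument is not reproduced, and the Schedule of Activities lists only modules; it also omits items such as risk aversion and access to protective equipment, which 9.4.1 shows are collected. Heads of household do answer for relatives on some health items, and the schedule marks the survey again at Month 6, although 5.5 describes it as one-time. What stands is narrower: the plan does not say that status or dates are captured for each person tested, and does not use them.
- The target antigen is not stated. If vaccines do not induce antibody to it, the trend problem disappears. This stands, and it is why the antigen must be stated first.
- A reader might infer that Hypothesis 3r is invalid or will come out with the wrong sign. The documents do not support this. The hypothesis and Model 3 are worded by serostatus, no planned variable classifies anyone as infected, and 2.2 reasons from receiving a positive result. A reversal needs assumed return rates and more seropositives than planned.
- The trend analysis is a single sentence in the secondary section. That limits its reach, but the readings it is meant to support appear in three sections of the protocol.

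**Conclusion.** The concern holds for interpreting the section 9.4.2 trends. Followed as written, those models cannot attribute a rise in seropositivity or IgG to infection, or a maintained value to persistence, if the assay detects vaccine antibody. On the stated assumptions the apparent Time 2 seroprevalence is 18.6% to 61.3% for 10% to 60% vaccinated between visits, against a true 10%. It stays at 10% if the assay does not react to vaccine antibody. Coverage and detection are assumptions throughout.

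For Hypothesis 3r, only the reading as an effect of past infection is affected, with size and direction undetermined. A reader might also suppose that the trial's main comparisons are compromised. They are not: Models 4a and 4b compare randomised arms on attendance and do not use serostatus.

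**What to change.** 1. State the target antigens of the IgG and IgM assays, and whether each detects vaccine-induced antibody.
2. At check-in for each antibody test, record for every person tested any COVID-19 vaccine dose and its date, reported by a parent for children.
3. In 9.4.2, report seroprevalence and the change in IgG and IgM by vaccination status: never vaccinated, vaccinated before Time 1, and vaccinated between visits. Base infection and waning statements on the never-vaccinated stratum, and say that this group is smaller and is selected on behaviour after Time 1.
4. For Hypothesis 3r, keep Model 3 as stated and add a sensitivity model with vaccination before Time 1 as a covariate. This leaves the stated contrast intact and avoids having to decide whether vaccinated positives are dropped or recoded.
5. If status cannot be collected, report seropositivity as infection or vaccination combined, and drop the infection-trend, waning and re-infection statements.

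The cost is one self-reported REDCap item per person per visit, some analysis-plan text, and less precise estimates within strata.

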7.1 DISCONTINUATION OF STUDY INTERVENTION/EXPERIMENTAL MANIPULATION

Participants who decline testing initially will be offered an exit survey which will ask them for reasons for declining. We will longitudinally follow the initial cohort that completed baseline survey (including people who declined testing in wave 1) and offer an additional wave of testing 6 months after the first wave.

Participants can choose to withdraw from the study at any time, and this will be documented in their REDCap record. When a subject discontinues Wave 2 retesting but not from the study, remaining study procedures (data analysis) will be completed as indicated by the study protocol.

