8 STUDY ASSESSMENTS AND PROCEDURES

8.1 ENDPOINT AND OTHER NON-SAFETY ASSESSMENTS

Households who are interested in participating will be assigned a household ID, and one adult from each household will complete the study survey questions. Household members interested in testing will then be assigned a unique Study ID and be scheduled for a testing appointment at a date and time convenient for them. Participants will be called with antibody test results within 5-7 days of initial test. Six months following initial test, participants will be asked to come in for Wave 2 retesting, where lotteries will be played and incentives realized. Participants will be called with antibody test results within 5-7 days of second test. All decisions related to participation and the scheduled appointment times will be documented within REDCap.

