9.2 SAMPLE SIZE DETERMINATION

We will recruit a cohort of 2,160 people (540 families), and stratify into 3 subgroups based on predictors of commitment to participation in testing programs. Randomization will be clustered by family. Sub-group membership will be based on the mean household survey response to the survey component. For the purposes of power analyses, we assume high Intra Cluster Correlation within family on uptake of repeat testing (>0.90).

Stratified Allocation Plan and Power Analysis (540 households, 2160 individuals)		
	Control	Intervention
Stratification	# households	# households
HTE Subgroup 1	60	60
HTE Subgroup 2	60	60

HTE Subgroup 3	60	60
% Seropositive in Baseline Test	10%	10%
Total Households Per Arm	180	180
Projected Average Treatment Effect Size	Reference Group	Reference+10%
Minimum Detectable Effect Size Compared to Controls (H4r)	±3%	
Detectable 3-subgroup HTE and Seropositivity (H1r, H2r, H3r)	±7%	

Assuming a similar effect size to prior studies in similar populations, we expect a 10 percentage point difference in repeat testing adherence between intervention and control groups. With 540 households, we are powered to detect as little as 3 percentage point difference between interventions and controls in the 540 households we will enroll. To assess heterogeneity of treatment effects (THE), there is more than 80% power to detect a between-subgroup difference of 7 percentage points, assuming 180 households in each sub-group.

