$$\pi = \beta_0 + \beta_1 x_{ij} + \eta_j + \varepsilon_i \quad [3]$$

For Hypothesis 3r, we will use a simple mixed-effects logistic model, where $\pi = \ln\left(\frac{p}{1-p_i}\right)$, is the probability of Time 2 attendance by individual i in household j given they attended Time 1 testing; β_1 is seropositivity status at Time 1 (yes vs. no); and η_j is the random intercept for each household capturing household-level effects.

We will use two separate models for Hypothesis 4r.

$$\pi = \beta_0 + \beta_1 x_{ij} + \beta_2 x_{ij} + \beta_3 x_{ij} + \beta_4 x_{ij} + \beta_5 x_{ij} + \eta_j + \varepsilon_i \quad [4a]$$

Model 4a will assess the probability, $\pi = \ln\left(\frac{p}{1-p_i}\right)$, of testing attendance for individual i in household j , where β_1 is the main effect for testing time (reference = Time 1); β_2 is the main effect for Financial Incentives (reference = lottery condition); β_3 is the main effect for Messaging (reference = personal); β_4 is the interaction between testing time and Financial Incentives; β_5 is the interaction between testing time and Messaging; and η_j is the random intercept for each household.

$$\pi = \beta_0 + \beta_1 x_{ij} + \beta_2 x_{ij} + \beta_3 x_{ij} + \beta_4 x_{ij} + \beta_5 x_{ij} + \beta_6 x_{ij} + \beta_7 x_{ij} + \eta_j + \varepsilon_i \quad [4b]$$

Model 4b will assess the probability, $\pi = \ln\left(\frac{p}{1-p_i}\right)$, of testing attendance for individual i in household j , where β_1 is the main effect for testing time (reference = Time 1); β_2 through β_4 are the main effects for study arm (personal messaging and loss protection, family messaging and lottery, family messaging and loss protection), where personal messaging and lottery is the reference group; β_5 through β_7 are the interactions between study arm and testing time; and η_j is the random intercept for each household.

For Models 4a and 4b, we will use unrestricted random sampling to select 3,000 observations, 2,000 times, clustered by household to bootstrap 95% confidence intervals for probability differences. We

will test differences in effect sizes for Model 4a (β_4 vs. β_5) and 4b (β_5 vs. β_6 ; β_5 vs. β_7 ; β_6 vs. β_7) using equality of regression coefficients tests.⁶ We will also calculate the inverse of observed probabilities to derive the Number Needed to Intervene on (NNI), and calculate standard errors by taking the square root of $P * (1 - P)/N$.⁷

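### The seropositivity, IgG and IgM trend models omit a person-level intercept, so the Time 1 to Time 2 change has too wide an interval and, if seropositive people return less often, a spurious decline

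*Combined protocol and SAP*

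**What the plan says.** Section 9.4.2 assesses seroprevalence trends with "separate hierarchical models with a random household intercept to regress seropositivity status (yes vs. no), IgG value, and IgM value on testing time" (Time 1 versus Time 2). It names no person term, within-person covariance, paired analysis, robust variance or missing-data method.

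The same people are sampled twice. Section 8.1 says "Six months following initial test, participants will be asked to come in for Wave 2 retesting", and section 2.1 says that "repeat antibody testing of those who were seropositive in the first wave of testing will allow us to test how well antibodies maintain their presence". Some Time 2 samples may be unpaired, because section 7.1 follows the whole surveyed cohort, "including people who declined testing in wave 1) and offer an additional wave of testing 6 months after the first wave".

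Hypothesis 3r in section 9.1 reads: "Persons who are sero+ at baseline will be less likely to return for a retest".

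The only resampling step is in section 9.4.1: "For Models 4a and 4b, we will use unrestricted random sampling to select 3,000 observations, 2,000 times, clustered by household". It does not extend to the trend models.

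**The concern.** With household as the only random effect, two samples from one person are modelled as no more alike than samples from two relatives. Two things follow.

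- **Precision.** Testing time varies within person. The stable person-level variance should cancel from the change, but here it is counted as noise. The interval is too wide and power to see a change is lost.
- **Selection.** If return depends on the Time 1 result, the Time 2 sample is selected on the outcome being modelled. A model that does not link a person's two samples cannot use a non-returner's own Time 1 value to correct for this, so part of the selection is read as a fall in seropositivity or antibody level.

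Section 9.4.2 gives the plan's only analysis of antibody results over time, and a spurious fall would look like waning.

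**Working it through.** The plan gives no power or precision figure for these models, so there is none to reproduce.

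**Inputs from the documents.** 540 households and 2,160 people, so 2,160/540 = 4 per household (section 9.2). Baseline seropositivity is 10% (allocation table, section 9.2).

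**Assumed, because the documents are silent.** Household/person/residual variance shares of 0.3/0.5/0.2, 0.3/0.3/0.4 and 0.6/0.2/0.2 on a unit-SD Gaussian scale. Logistic random-effect SDs of 1.5 (household) and 1.8 (person). Return rates (seropositive/seronegative) of 100/100, 60/60, 40/60 and 30/70%. The true change is zero throughout.

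**Step 1: standard error with complete pairs.** With n people and known variances:

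- household-only model: SE = sqrt(2 × (person + residual)/n)
- true value: SE = sqrt(2 × residual/n)
- ratio = sqrt((person + residual)/residual)

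For 0.3/0.5/0.2 the SEs are sqrt(2 × 0.7/2160) = 0.0255 and sqrt(2 × 0.2/2160) = 0.0136, a ratio of sqrt(0.7/0.2) = 1.87. The other ratios are sqrt(0.7/0.4) = 1.32 and sqrt(0.4/0.2) = 1.41.

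When the variances are estimated, the household term absorbs a little of the person variance. Of the 28 pairs among a household's 8 samples, 4 are same-person. The fitted residual is therefore about 0.7 - 0.5 × 4/28 = 0.629, and the SE is sqrt(2 × 0.629/2160) = 0.0241. Simulation with fitted variances (300 replicates) gave the same 0.0241, against a sampling SD of 0.0140: a ratio of 1.72. For 0.3/0.3/0.4 it gave 1.36.

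**Step 2: standard error at 60% return, unrelated to serostatus.** Model SE divided by sampling SD:

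- Continuous, known variances: about 1.5, 1.2 and 1.3 for the three sets of shares in the order above.
- Continuous, fitted variances: 0.0285/0.0194 = 1.47 and 0.0290/0.0240 = 1.21 (first two sets).
- Logistic seropositivity: 0.123/0.108 = 1.14. With full return it is 0.106/0.088 = 1.20.

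There is no bias in these scenarios, and the false-positive rate is 0-3%, so the error is conservative.

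**Step 3: return that depends on the Time 1 result.** At 40% versus 60%, the seropositive share of returners by Time 1 status is 0.1 × 0.4/(0.1 × 0.4 + 0.9 × 0.6) = 0.04/0.58 = 6.9%. At 30% versus 70% it is 0.03/0.66 = 4.5%. That is the crude selection away from 10%; a household intercept removes only part of its effect. Household-only results:

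| Outcome, shares | Bias 40/60 | False positives 40/60 | Bias 30/70 | False positives 30/70 |
|---|---|---|---|---|
| Continuous 0.3/0.5/0.2 | -0.03 SD | 8-9% | -0.05 SD | 44-47% |
| Continuous 0.3/0.3/0.4 | -0.02 SD | 5-7% | -0.03 SD | 15-16% |
| Continuous 0.6/0.2/0.2 | -0.01 SD | about 4-5% | -0.02 SD | about 11% |
| Logistic seropositivity | log-OR -0.11 | 12% | log-OR -0.18 | 31% |

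Where two values appear, they come from runs with known and with fitted variances; the third set was run with known variances only.

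**Step 4: with a person-within-household intercept.** In the fitted runs, linear-model bias is within 0.003 SD, SE/sampling SD is 0.97-1.11 and the false-positive rate is 3-6%. The logistic log-OR is within about 0.01 of zero, with 5-6% false positives.

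**Step 5: what the added term does to the odds ratio.** A fall from 10% to 5% is a population log-OR of ln(0.05/0.95) - ln(0.10/0.90) = -0.75. With random-effect SDs of 1.5 and 1.8, the person-specific log-OR for the same fall is -1.10. The added term therefore changes what the coefficient means.

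**The case against.** *Hierarchical could include a person level.* Possibly, but household is the only level named, and Models 3, 4a and 4b in section 9.4.1 also carry only the household term. If a person level is intended, the plan should say so.

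*The sizes rest on assumptions.* This stands. Neither the variance shares nor the return rates are in the documents, and a Gaussian IgG is a strong assumption when about 10% are seropositive. Ranges are therefore given. The direction does not depend on the particular values: the complete-pairs SE is inflated whenever person variance exceeds zero, and the bias was downward in every scenario with lower seropositive return.

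*The two faults partly offset each other.* This stands. A reader might set the bias of -0.03 SD against the person-intercept SE of 0.017 and infer an error of nearly two SEs. The planned model would report about 0.030, so the bias is about one of its own SEs or less. At 40% versus 60% the continuous false-positive rate stays close to nominal.

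*Selective return is not established.* This stands. A reader might take it as fact, but 3r is a hypothesis and section 2.2 says only that a positive result could reduce willingness to retest.

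*The waves do not compare different people.* A reader might infer that they largely do. In the 40/60 scenario every Time 2 person also has a Time 1 sample, and 0.1 × 0.4 + 0.9 × 0.6 = 58% of Time 1 people are in both waves.

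*The models are not the direct test of waning.* This stands. Section 9.4.2 describes seroprevalence trends and pools everyone tested, so new infection and waning are mixed. The question in section 2.1 concerns those seropositive at the first wave, and a person intercept alone does not answer it.

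**Conclusion.** The point holds, as a secondary-analysis fault of modest and conditional size. The planned standard error of the change is too large: about 1.2 to 1.5 times its sampling SD at 60% return and up to about 1.9 times with complete pairs for IgG and IgM, and about 1.1 to 1.2 times for logistic seropositivity. If return is unrelated to serostatus, that is the only fault.

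If seropositive people return less often, a spurious decline is added. It is small at 40% versus 60%. At 30% versus 70% it is material, with false-positive rates of about 11-47% depending on the outcome and variance shares. The direction is secure; the sizes depend on the assumed shares and return rates.

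A reader might infer that the incentive and messaging results are compromised too. The documents do not support that: H4r does not use these models, no hypothesis in section 9.1 concerns a seroprevalence trend, and no power is claimed for one.

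**What to change.** In section 9.4.2:

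1. Add a random intercept for person nested within household to the seropositivity, IgG and IgM models.
2. Keep the Time 1 values of people who do not return in the fit.
3. For seropositivity, report the change as a marginal (population-averaged) prevalence difference standardised from that model. The person-specific odds ratio is not the seroprevalence trend.
4. State that this handles return that depends on the observed Time 1 result, and not return that depends on unobserved Time 2 status.

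The cost is a wording change, one extra term per model and a standardisation step for seropositivity. No new data are needed.
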